4.3.5 Planned sample size

The primary hypothesis is that ^{99m}Tc-rhAnnexin V-128 carotid imaging can detect apoptosis. We anticipate that the prevalence of positive ^{99m}Tc-rhAnnexin V-128 carotid scans will be about 0.3 to 0.5 of the patients. A sample size of 30 patients produces a 95% confidence interval with a precision of about 0.17 to 0.20 when the estimated proportion is 0.3 to 0.5. Sample size was also estimated for the comparison of ^{99m}Tc-rhAnnexin V-128 uptake in asymptomatic or symptomatic with TIA patients with carotid disease versus normals using a 5% significance level and power of 95%. The measured neck uptake in 12 normals was 0.8 ± 0.27% ID/gm in the Phase I study. Assuming a similar SD of 0.27% ID/gm in the patients and a minimal clinically important difference (MCID) of

²Anti-rhAnnexin V-128 IgG and IgM antibodies will be quantified in serum samples by ELISA. For this purpose 10 mL blood samples will be collected at screening and Day 30 (±3 days) post administration of investigation product. Serum will be prepared, divided into six aliquots and frozen (-80°C). Three out of six serum samples per time-point will then be shipped to the central laboratory.

³Within 8 weeks prior to ^{99m}Tc-rhAnnexin V-128 SPECT imaging.

Version: 01 Page: **22 of 167**

50% or a change of 0.4 in uptake, the required sample size is 9 normals and 25 patients. Allowing for attrition, we plan to recruit 10 normals and 35 patients.

5 SUBJECT POPULATIONS (ANALYSIS SETS)

5.1 Efficacy

5.1.1 Full analysis set (FAS)

In accordance with the Intention To Treat (ITT) principle, the FAS population includes all subjects who received the study drug and completed the ^{99m}Tc-rhAnnexin V-128 imaging procedure.

5.1.2 Per Protocol population (PP)

All subjects in the FAS population for whom no major protocol violations/deviations occurred. The criteria defining the major protocol deviations will be established before the data base locking.

5.2 Safety set

The safety population is made up of all subjects who received the administration of ^{99m}Tc-rhAnnexin V-128.

5.3 Primary population

The primary and secondary efficacy analysis will be based on the FAS population.

The primary efficacy analysis on the Primary endpoint of Phase II will be also performed on the PP population as supportive analysis.

The assessment of safety and tolerability will be based on the Safety population.

Version: 01 Page: **24 of 167**

6 STATISTICAL METHODS

6.1 Statistical analysis strategy

The statistical analyses will be performed in accordance with the principles of ICH E9 guideline and the guideline on clinical evaluation of diagnostic agents and they will be based on data from the study site, unless otherwise stated.

The statistical analysis will be performed by ______ - Italy

6.1.1 General statistical considerations

For continuous variables, descriptive summary statistics will include the number of non-missing values, number of missing values, mean, standard deviation, 95% 2-sided confidence interval, median, lower and upper quartile, minimum and maximum. Box plot graphs will also be presented when appropriate.

For categorical variables, descriptive summary statistics will include counts and percentages per category.

For analysis purposes, baseline for a given assessment will be defined as the last non-missing value prior to the administration of ^{99m}Tc-rhAnnexin V-128, unless stated otherwise.

6.1.2 Efficacy endpoint(s)

6.1.2.1 Primary endpoint of PoC

The feasibility of imaging apoptotic activity in carotid atherosclerotic plaques using ^{99m}Tc-rhAnnexin V-128 will be assessed by the data monitoring committee (visual image review and consensus) using the first 15 patient and 5 control scans.

The frequency and severity of abnormal carotid scans will be determined in the patient and control groups by review of the number, localization, length and uptake intensity grade of each plaque to define a positive or negative scan at each time point.

DMC outputs were defined in the DMC charter.

6.1.2.2 Primary endpoint of Phase II

The primary endpoint of Phase II is the prevalence of abnormal ^{99m}Tc-rhAnnexin V-128 Planar and SPECT/CT scans in patient and control groups.

The prevalence of apoptotic activity is defined as the proportion of patients with "abnormal" SPECT imaging scans (also described as positive scans). Activity concentrations (MBq/cc or % injected dose/gram) determined from reconstructed image counts as described in section 4.3.3.3 will be compared with the normal database of carotid and aortic uptake from the 10 control participants and used to identify abnormal uptake in carotid artery disease participants that will define an abnormal SPECT/CT result.

The prevalence of abnormal ^{99m}Tc-rhAnnexin V-128 scans will be reported with the related 95% C.I. for both carotid participating group and the control group at each time point and overall.

The overall result of ^{99m}Tc-rhAnnexin V-128 imaging will be unique: patients with at least one SPECT/CT positive result (after 60 min or after 120 min from ^{99m}Tc-rhAnnexin V-128 injection) will be considered as abnormal, patients with both SPECT/CT images negative will be considered as normal.

The results of ^{99m}Tc-rhAnnexin V-128 will also be reported in contingency tables as normal and abnormal for each group (patient and control) at each time point (60 min and 120 min after injection) in order to assess where any difference between the time points occurred.

Results of Carotid Ultrasound and SPECT procedures will be included in the data listing. The listings will also flag which patients had a history of TIA.

The primary efficacy analysis will be performed on the FAS population.

6.1.2.3 Secondary endpoints

The secondary endpoints of Phase II and the related statistical analysis are:

- Descriptive statistics of ^{99m}Tc-rhAnnexin V-128 uptake in patients vs control participants will be presented by areas of interest (left carotid, right carotid, thoracic aorta, abdominal aorta and aortic arch) and by time points to assess the background uptake profile and the pathologic profile. Comparison of uptake in patients vs controls at each timepoint will be explored by the most appropriate test i.e. two sample t-test.
- The relationship between carotid uptake (separately for left and right) and ultrasound grade of plaque echolucency/echogenicity (1 echolucent, 2 predominantly echolucent, 3 predominantly echogenic, 4 echogenic) will be assessed for all patients using box plots and

Version: 01 Page: **26 of 167**

summaries of uptakes by the levels of echolucency/echogenicity for each time point. Only carotids with stenosis (defined as \geq 50% as per protocol) will be included in this analysis (i.e. a patient with only 1 carotid with stenosis \geq 50% will contribute data for that carotid uptake value and the associated plaque echolucency/echogenicity value for the same carotid, patients with stenosis in both carotids will contribute data on uptake and echolucency/echogenicity for each of their carotids).

Association between carotid and aortic uptake will be assessed for patients and controls, by time
point, using scatter plots. All carotids with ≥ 50% stenosis (as described above) will be included
in this plot, and different colours/symbols will be used for left and right carotid results. If further
investigation is considered appropriate, the correlation coefficients (Pearson's or Spearman's)
within left carotids and right carotids separately will be calculated.

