8.1 Inclusion criteria

For all participants:

1. Males and females age 18 years or greater;
2. Able and willing to comply with the study procedures;
3. Negative pregnancy test for women of childbearing potential at screening and on the day of administration of ^{99m}Tc-rhAnnexin V-128.

For participants with carotid artery disease:

4. Evidence of 50% or more carotid stenosis in one or more carotid arteries on carotid ultrasound within 10 years;

For control participants:

4. No significant carotid artery disease on carotid ultrasound;

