12.1 Sample size and analysis

The primary hypothesis is that ^{99m}Tc -rhAnnexin V-128 SPECT carotid imaging can detect apoptosis. We anticipate that the prevalence of positive ^{99m}Tc -rhAnnexin V-128 SPECT carotid scans will be about 0.3 to 0.5 of the patients. A sample size of 30 patients produces a 95% confidence interval with a precision of about 0.17 to 0.20 when the estimated proportion is 0.3 to 0.5. Sample size was also estimated for the comparison of ^{99m}Tc -rh-Annexin-V 128 uptake in asymptomatic patients with carotid disease versus normals using a 5% significance level and power of 95%. The measured neck uptake in 12 normals was $0.8 \pm 0.27\%$ ID/gm in the Phase I study. Assuming a similar SD of 0.27% ID/gm in the patients and a minimal clinically important difference (MCID) of 50% or a change of 0.4 in uptake, the required sample size is 9 normals and 25 patients. Allowing for attrition, we plan to recruit 10 normals and 35 patients.

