6.1.20 Significance testing and estimation

All statistical tests will be two-sided at the 5% level of significance.

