		95% C.I.	99.9 - 99.9	99.9 - 99.9
	Negative	n (%)	99 (99.9)	99 (99.9)
	Missing	n (%)	99 (99.9)	99 (99.9)

Source: Data listings {Specify data listing number(s)} Analysis dataset: {Specify datasets}

Notes: All percentages are based upon the number of enrolled subjects by group.

Confidence intervals are estimated using the exact (Clopper-Pearson) formula for binomial proportions.

^{*} Patient = Subject with asymptomatic plaque; Control = Healthy volunteer

[#] Subjects with either a positive scan at 60 or 120 minutes post injection will be considered overall positive

Version: 01 Page: **93 of 167**

Table 14.2.1.3: Patient Carotid and Aorta Imaging Assessment – Comparison between time points – FAS Population

60 MINS AFTER IP INJECTION	120 MINS AFTER IP INJECTION	STATISTIC	PATIENT* (N=xx)
Positive	Positive	n (%)	99 (99.9)
Positive	Negative	n (%)	99 (99.9)
Positive	Total	n (%)	99 (99.9)
Negative	Positive	n (%)	99 (99.9)
Negative	Negative	n (%)	99 (99.9)
Negative	Total	n (%)	99 (99.9)
Total	Positive	n (%)	99 (99.9)
Total	Negative	n (%)	99 (99.9)
Total	Total	n (%)	99 (99.9)
		p-value	0.9999

Source: Data listings {Specify data listing number(s)} Analysis dataset: {Specify datasets}

Notes: All percentages are based upon the number of subjects who performed both imaging procedures.

p-value is based on McNemar's test.

^{*} Patient = Subject with asymptomatic plaque

Version: 01 Page: **94 of 167**

Table 14.2.1.4: Left Carotid Uptake Imaging Assessment – Target to Background Ratio (TBR) – FAS Population

TIME POINT	STATISTIC	PATIENT* (N=xx)	CONTROL* (N=xx)
60 mins after IP injection	n	99	99
	Missing	99	99
	Mean	99.9	99.9
	S.D.	99.9	99.9
	Median	99.9	99.9
	Q1, Q3	99.9, 99.9	99.9, 99.9
	Min, Max	99, 99	99, 99
	p-value^		0.9999
120 mins after IP injection	n	99	99
•	Missing	99	99
	Mean	99.9	99.9
	S.D.	99.9	99.9
	Median	99.9	99.9
	Q1, Q3	99.9, 99.9	99.9, 99.9
	Min, Max	99, 99	99, 99
	p-value^		0.9999

Source: Data listings {Specify data listing number(s)} Analysis dataset: {Specify datasets}

^p-value is based on T- test.

^{*} Patient = Subject with asymptomatic plaque; Control = Healthy volunteer

Version: 01 Page: **95 of 167**

Table 14.2.1.5: Right Carotid Uptake Imaging Assessment – Target to Background Ratio (TBR) – FAS Population

TIME POINT	STATISTIC	PATIENT* (N=xx)	CONTROL* (N=xx)
60 mins after IP injection	n	99	99
	Missing	99	99
	Mean	99.9	99.9
	S.D.	99.9	99.9
	Median	99.9	99.9
	Q1, Q3	99.9, 99.9	99.9, 99.9
	Min, Max	99, 99	99, 99
	p-value^		0.9999

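### The exploratory patient-control carotid comparison is run by side over the whole FAS, so carotids below 50% stenosis in patients with one-sided disease count as patient uptake and dilute the contrast

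*SAP*

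**What the plan says.** Protocol 8.1, repeated in SAP 4.2.1.1, admits a patient on "Evidence of 50% or more carotid stenosis in one or more carotid arteries on carotid ultrasound within 10 years". One-sided disease is enough.

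The first secondary bullet of SAP 6.1.2.3 describes uptake in patients and controls by area, with left and right carotid as separate areas, and adds: "Comparison of uptake in patients vs controls at each timepoint will be explored by the most appropriate test i.e. two sample t-test". It sets no stenosis condition. The matching shells in SAP 11.2 are Table 14.2.1.4, "Left Carotid Uptake Imaging Assessment – Target to Background Ratio (TBR) – FAS Population", and its right-sided twin, Table 14.2.1.5. Each carries a t-test p-value at each time point and neither has a stenosis footnote. The FAS (SAP 5.1.1) is defined by dosing and completed imaging, with no criterion at artery level.

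The second bullet, on echogenicity, does limit the arteries. Only carotids with at least 50% stenosis "will be included in this analysis (i.e. a patient with only 1 carotid with stenosis" at that level gives data for that carotid alone). The third bullet, on carotid and aortic uptake, applies the same limit to its plot. In the shells, the stenosis footnote stands only under Tables 14.2.1.9 and 14.2.1.10, where the cut-off is written as above 50% rather than at least 50%.

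Protocol 12.1 and SAP 4.3.5 give two grounds for the sample size: the precision of the prevalence estimate, and the patient-control uptake comparison.

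**The concern.** Patients are selected by person, but the comparison is made by side. Side plays no part in any hypothesis; stenosis does. Where disease is one-sided, the patient column for the other side holds an artery that did not qualify the patient. If such arteries take up less tracer than stenosed ones, as the trial's premise suggests, the mean difference from controls shrinks and the spread among patients grows.

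The bullet is meant to describe both background and pathologic uptake. Protocol 12.4 intends the inferential results as a basis for later confirmatory trials. A difference weakened by the choice of artery would pass misleading information to those trials, on the comparison that was used to plan patient and control numbers.

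**Working it through.** **Inputs.** SD: "Assuming a similar SD of 0.27% ID/gm in the patients" (Protocol 12.1). Difference: "minimal clinically important difference (MCID) of 50% or a change of 0.4 in uptake" (same section). Error rates: "using a 5% significance level and power of 95" per cent (same section). Sidedness: "All statistical tests will be two-sided at the 5% level of significance" (SAP 6.1.20). Planned recruitment: 35 patients and 10 controls.

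**The plan's own figure.** With k = 25/9 patients per control, controls = (1 + 1/k)(1.960 + 1.645)² × 0.27²/0.4² = 1.36 × 12.995 × 0.4556 = 8.05, rounded up to 9. Patients = 9 × 25/9 = 25. The stated 9 and 25 are reproduced. Power at 35 v 10 is 98.1% by the noncentral t. This calculation gives every analysed patient value the full 0.4 difference.

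**Dilution by side.** Let b be the share of patients with bilateral disease. The documents do not give it, so a range is used. With one-sided disease split evenly between left and right, the share of patient carotids on a given side that are stenosed is f = b + (1 − b)/2 = (1 + b)/2. Suppose arteries below 50% behave like control arteries. Then:

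- mean difference = 0.4 × f
- patient SD = √(0.27² + f(1 − f) × 0.4²)

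Power comes from simulating the pooled two-sample t-test at 35 v 10 (40,000 runs). The chance that both sides miss at one time point comes from simulating the two sides jointly (20,000 runs), with an assumed within-person left-right correlation of 0 to 0.8.

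| Bilateral share b | f | Mean difference | Patient SD | Power per side | Both sides miss, one time point |
|---|---|---|---|---|---|
| 0% | 0.5 | 0.20 | 0.336 | 38% | 37–48% |
| 20% | 0.6 | 0.24 | 0.334 | 53% | 20–32% |
| 40% | 0.7 | 0.28 | 0.326 | 69% | 9–19% |
| 60% | 0.8 | 0.32 | 0.314 | 83% | 3–9% |
| 100%, or one stenosed artery per patient | 1 | 0.40 | 0.27 | 98% | not applicable |

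**Milder assumption.** If arteries below 50% carry half the excess (0.2), the mean difference is 0.4f + 0.2(1 − f) = 0.2 + 0.2f, that is 0.30, 0.32, 0.34 and 0.36. Power per side is then about 83%, 88%, 91% and 94%.

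**Check of the remedy.** Comparing one stenosed carotid per patient with each control's left-right mean, by an unequal-variance t-test, gave a simulated false-positive rate of about 5%. Power was about 97% or more across the left-right correlations tried.

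**The case against.** The strongest reply is that little rests on this comparison. The secondary objectives are control uptake, uptake against echogenicity, and the carotid-aortic relation. No objective or hypothesis is a patient-control test. Protocol 12.4 asks only for control descriptives, the SAP presents the comparison as exploratory, and the primary endpoint is prevalence. All of that stands. A reader might infer that a trial objective depends on this contrast; the documents do not support that. They do use it as one of two grounds for the sample size, and they tabulate p-values for it.

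SAP 6.1.17 allows stenosis level to be explored as a covariate, and Listings 16.2.4.2 and 16.2.6.2 give stenosis and uptake by side. A restricted reading could therefore be recovered. But 6.1.17 is discretionary and requires nothing, and a listing is not an analysis.

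The low power figures are worst case, since arteries below 50% may hold plaque. The 98% comparator is also optimistic: it gives every stenosed artery the 0.4 shift, while Protocol 5.1 expects a prevalence of only 0.3 to 0.5. Planning was in % ID/gm of neck uptake, while the tables use target-to-background ratio. These points limit what the numbers can show. They do not change the direction as long as stenosed arteries take up more tracer.

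A reader might also infer that the SAP saw the dilution and forgot to deal with it here. The text does not show that: pairing uptake with a plaque grade is reason enough for the limit in the second bullet. Finally, the use of every carotid is read from the absence of a restriction and from the FAS shells; the SAP does not say it in words. No other rule is given.

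**Conclusion.** The point holds as a shortcoming of an exploratory secondary analysis that is cheap to put right. Followed as written, the plan mixes stenosed and non-qualifying carotids in the patient groups of Tables 14.2.1.4 and 14.2.1.5. The loss runs from none, if all disease is bilateral or if arteries below 50% take up as much tracer as stenosed ones, to a fall in per-side power from about 98% to about 38%, if all disease is one-sided and those arteries show no excess. The second figure is an upper bound on the loss on the planning scale, not an estimate for this trial.

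Two stronger readings should be resisted. The sample size is not miscalculated: 9 and 25 follow from its inputs. Nor does the per-side figure mean that a true signal would usually be missed on both sides. Even in the worst case shown, that chance at one time point is 37–48%, and the second time point can only lower the chance of missing throughout.

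**What to change.** In the first bullet of SAP 6.1.2.3, add a carotid comparison with one value per patient. Take the index carotid, meaning the one with at least 50% stenosis on ultrasound, or the more stenosed if both qualify. Compare it with the mean of left and right in each control, by an unequal-variance t-test at each time point. The choice uses CU_STEN_R and CU_STEN_L, which are already collected, so it does not depend on uptake, and every patient with a confirmed stenosis stays in.

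Keep the left and right tables as descriptive displays and show the stenosis status of each artery. Whether they keep their p-values is a matter of preference. Use one cut-off throughout, since SAP 6.1.2.3 says at least 50% and the footnotes to Tables 14.2.1.9 and 14.2.1.10 say above 50%.

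A simpler alternative is to apply the existing 50% rule within each side. With all disease one-sided, that leaves about 18 patients against 10 controls per side and about 95% power on the planning values, but it keeps two tests per time point.

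The cost is a wording change and one extra table, with no new data or patients. The drawback is that a control's two-artery mean is slightly less variable than a single artery, which the unequal-variance test allows for.

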10.5 Ultrasound Examination

Clinical evidence of 50% or more carotid stenosis in one or more carotid arteries on carotid ultrasound within 10 years prior to enrolment is required for inclusion in the trial.

Evidence of 50% or more carotid stenosis has to be confirmed in a more recent US imaging within 8 weeks prior to ^{99m}Tc -rhAnnexin V-128 administration. If not confirmed, the participant will be declared as a screening failure.

B-mode and color Doppler ultrasound studies will be acquired of both carotid arteries and performed with an ultrasound scanner equipped with a 5- to 7-MHz transducer. Plaque morphology, as echogenicity, defined as reflectance of the emitted ultrasound signal, will be assessed as previously described²⁹ and graded from 1 to 4 as echolucent, predominantly echolucent, predominantly echogenic, or echogenic. The vessel lumen will be used as the reference structure for defining echolucency, and the bright echo zone produced by the media-adventitia interface in the far wall will be used as the reference structure for defining echogenicity. Interobserver reproducibility of plaque morphology in stenotic arteries has been previously assessed ($\kappa=0.56$, 95% CI 0.38 to 0.74)³¹.

The degree of stenosis will be calculated by the following equation: $(1 - \text{PSV}_r / \text{PSV}_s) \times 100\%$, where PSV_r denotes peak systolic velocity at the point of reference (here, the distal carotid artery) and PSV_s the peak systolic velocity in the stenosis³¹.

11. Data Monitoring Committee

The Data Monitoring Committee (DMC) consists of investigators and Sponsor representatives, as well as external persons such as independent experts, if deemed necessary by the Sponsor. The DMC will review and evaluate the images of the first 15 patients and the first 5 healthy participants in terms of image quality, carotid target uptake and clinical relevance of the study product. The DMC will also review the safety data. The frequency of abnormal carotid scans will be determined in the participant and normal groups. The study will be terminated if there is a low frequency of positive scans in the carotid participant group or high frequency of positive scans in the normal group.

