12.2 General statistical considerations

Statistical methods will be detailed in the Sponsor statistical analysis plan.

Continuous variables will be presented as number of non-missing values, mean, standard deviation, median, minimum, maximum and quartiles. For categorical variables, descriptive statistics will include counts and percentages per category. Confidence intervals will be computed when appropriate. Continuous variables will be compared using the most appropriate test such as paired analysis Mann-Whitney-Wilcoxon U test or paired analysis student-t test. Proportions will be compared using the most appropriate test such as Chi squared test, fisher exact test or McNemar test. Pearson's or Spearman linear regression analysis will be used to calculate the relationship between two data sets as appropriate. A p value less or equal to 0.05 will be considered significant.

No adjustment for multiplicity will be applied and missing data will not be replaced.

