12.4 Efficacy

Primary endpoint of PoC:

The feasibility of imaging apoptotic activity in carotid atherosclerotic plaques using ^{99m}Tc-rhAnnexin V-128 will be determined by the data monitoring committee (visual image review and consensus).

Primary endpoint of Phase II:

Efficacy of ^{99m}Tc-rhAnnexin V-128 planar and SPECT/CT imaging will also be evaluated by determining the prevalence of abnormal ^{99m}Tc-rhAnnexin V-128 scans.

Secondary endpoints:

Descriptive statistics of ^{99m}Tc-rhAnnexin V-128 uptake in control subjects will be presented by areas of interest to assess the background uptake profile.

^{99m}Tc-rhAnnexin V-128 uptake will be related to ultrasound data of plaque echogenicity and echolucency, by direct comparison and by using correlation test and/or diagnostic test performance methods (McNemar test) if appropriate.

^{99m}Tc-rhAnnexin V-128 uptake in carotids will be correlated to its aortic uptake in all participants.

Efficacy analysis of the primary endpoint will be mainly descriptive in nature. Inferential statistics (such as comparisons, correlations...) will be mainly conducted as explorative analyses to serve as the basis for future confirmatory trials.

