4.1.2.1 Secondary hypotheses

- ^{99m}Tc-rhAnnexin V-128 uptake will be increased in plaque with greater echogenicity.
- 99mTc-rhAnnexin V-128 uptake will be decreased in plaque with greater echolucency.
- 99mTc-rhAnnexin V-128 imaging can be used to detect apoptosis in the aorta in asymptomatic patients with at least one 50% carotid stenosis as defined by ultrasounds.
- Aortic uptake of ^{99m}Tc-rhAnnexin V-128 will be correlated with carotid uptake of ^{99m}Tc-rhAnnexin V-128.

Version: 01 Page: **15 of 167**

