8 CHANGES FROM PROTOCOL

No changes from the protocol were made.

Statistical Analysis Plan ANNEXIN 04 Confidential

Version: 01

Page: **35 of 167**

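### No estimate of association is pre-specified for uptake versus plaque echogenicity, and the protocol's optional correlation test is dropped without explanation

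*SAP*

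**What the plan says.** Both documents list uptake versus plaque echogenicity and echolucency as a secondary objective (Protocol section 4, SAP 4.1.2). Two directional hypotheses go with it: "uptake will be increased in plaque with greater echogenicity" and "uptake will be decreased in plaque with greater echolucency" (SAP 4.1.2.1, repeating Protocol 5.2). Plaques are "graded from 1 to 4 as echolucent, predominantly echolucent, predominantly echogenic, or echogenic" (Protocol 10.5), so both hypotheses refer to a single ordered scale.

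Protocol 12.4 says uptake will be related to the ultrasound grade "by direct comparison and by using correlation test and/or diagnostic test performance methods (McNemar test) if appropriate". Protocol 12.2 adds that "Pearson's or Spearman linear regression analysis will be used to calculate the relationship between two data sets as appropriate" and leaves the detail to the SAP. Protocol 12.4 also states that inferential analyses, with correlations given as an example, "will be mainly conducted as explorative analyses to serve as the basis for future confirmatory trials".

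SAP 6.1.2.3 assesses the relationship by box plots and "summaries of uptakes by the levels of echolucency/echogenicity for each time point", with left and right carotids handled separately and only arteries with at least 50% stenosis included. The shells for Tables 14.2.1.9 (left) and 14.2.1.10 (right) hold n, missing, mean, SD, median, quartiles and range for each grade at 60 and 120 minutes. They have no row for a coefficient, trend, interval or p-value. SAP section 8 reads "No changes from the protocol were made".

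**The concern.** The hypotheses are about direction: does uptake rise or fall along the grade? The planned output describes uptake within each grade and never combines the grades into an estimate of that movement. The reader must compare four small columns, on each of two sides, at each of two time points.

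The neighbouring items in SAP 6.1.2.3 are treated differently. Patient-versus-control uptake gets a t-test, with p-value rows in Tables 14.2.1.4 to 14.2.1.8. Carotid-versus-aortic uptake gets scatter plots and, if thought appropriate, correlation coefficients. Only the echogenicity question has no statistic at all, and no reason is given. A later confirmatory trial would need an effect size with its uncertainty, and this plan does not supply one.

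**Working it through.** **The plan's own figure.** No sample size, power or precision is stated for the echogenicity question. The nearest stated figure is for patients versus normals (Protocol 12.1): SD 0.27, difference 0.4, two-sided 5%, 95% power, 9 normals and 25 patients. With ratio k = 25/9,

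n(normals) = (1.960 + 1.645)² × 0.27² × (1 + 1/k) / 0.4² = 13.0 × 0.4556 × 1.36 ≈ 8.05, rounded up to 9, which gives 25 patients.

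It reproduces (power 0.968 by the normal approximation, 0.959 by the noncentral t). It supports a different comparison and says nothing about a trend over grades.

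**Artery counts (assumed).** The planned 35 patients each have at least one artery with 50% stenosis or more. The bilateral rate is not given. With no bilateral disease there are 35 eligible arteries. With 15 of 35 bilateral (43%) there are 50. Split evenly by side, that is about 18 to 25 per side. Spread evenly over four grades, 18/4 to 25/4 is roughly 4 to 6 arteries per cell.

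**Power and precision of a rank correlation.** Assume a true rho of 0.4 (not in the documents) and a two-sided 5% test (SAP 6.1.20). On the Fisher scale, z = atanh(0.4) = 0.4236 and SE = √(1.06/(n − 3)), where 1.06 is the Spearman variance factor. Power = Φ(z/SE − 1.96). The 95% interval for an observed 0.4 is tanh(z ± 1.96 SE). The smallest rho detectable with 80% power is tanh(2.80 SE).

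| n | z/SE | Power | 95% CI if 0.4 observed | Detectable rho |
|---|---|---|---|---|
| 18 (one side) | 1.59 | 36% | −0.10 to 0.74 | 0.63 |
| 25 (one side) | 1.93 | 49% | −0.01 to 0.69 | 0.55 |
| 35 (pooled, one artery each) | 2.33 | 64% | 0.07 to 0.65 | 0.47 |
| 50 (pooled, treated as independent) | 2.82 | 81% | 0.13 to 0.62 | 0.40 |

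The last row is a best case: 50 arteries from 35 patients are not independent.

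**Cross-check by simulation.** There were 3,000 runs per scenario, with 35 patients, four roughly equal grades, within-patient correlation 0.5 and 0% to 50% bilateral disease, all assumed. At an underlying correlation of 0.4, one Spearman test with one averaged value per patient had power of about 0.58. Each side alone had 0.31 to 0.45. With no association, the chance that at least one side reached p < 0.05 was about 10%, as expected from 1 − 0.95² = 0.0975. Testing the two sides separately and taking either would therefore gain power only by raising the error rate.

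**The case against.** The strongest reply is that the protocol promised little. Its wording is a menu with a condition, it leaves methods to the SAP, and it calls inferential work mainly exploratory. The SAP keeps the direct comparison and leaves out an option. This stands. A reader might infer that the SAP abandoned a committed analysis and that section 8 is plainly false, but the documents do not support that. What they show is a named option omitted with no reason, and a section 8 that does not say how the condition was resolved.

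Second, the SAP does not offer pictures alone, since means, SDs and medians by grade are planned at both time points. That also stands. A reader might infer that the trial can say nothing about uptake by grade, but it will describe uptake within grades. What is missing is an estimate of the association.

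Third, splitting by side has a statistical use: it keeps one artery per patient in each display, and no artery is discarded. The SAP does not give this reason, but it is a sensible one, so the split should not be called baseless. It still leaves two imprecise pictures of one question, and a patient-level bootstrap handles the clustering without it.

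Finally, SAP 10.7 allows further methods if justified, and Proc Corr is in the program list in SAP 12.2. Neither pre-specifies this analysis. The only correlation the SAP describes is carotid versus aortic.

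**Conclusion.** The point holds as a gap in a secondary, exploratory analysis: the SAP states a method that yields no estimate of association for a named objective. The two hypotheses are mirror images on one 1 to 4 grade, so this is one question, and one signed estimate would address both. The primary endpoint and the continuation decision do not depend on it.

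The power figures are illustrative. They rest on an assumed 35 to 50 stenotic arteries, an even split by side and a true rho of 0.4, and they describe a test that the SAP does not currently plan. A reader might infer that pooling makes the question well powered. It does not: with one artery per patient, 80% power needs a rho of about 0.47. Pooling mainly improves precision. An observed 0.4 would carry an interval that excludes zero at 35 arteries, but not at 18 or 25.

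**What to change.** Add to SAP 6.1.2.3 one exploratory artery-level estimate at each time point, pooling left and right carotids with stenosis of at least 50%. Use Spearman's rho between uptake and grade 1 to 4, with a 95% confidence interval from a bootstrap that resamples patients. A regression of uptake on grade with patient-clustered standard errors is an alternative, but it treats the grades as equally spaced. Label the result exploratory and add one table shell.

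Keep the box plots and the side-specific summaries. Correct section 8 to say how the protocol's conditional correlation and McNemar options were resolved. While editing, reconcile the footnotes of Tables 14.2.1.9 and 14.2.1.10, which say stenosis above 50%, with the text of 6.1.2.3, which includes 50%.

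The cost is a sentence or two in the SAP, one table and a short program, with no new data. The downside is one more unadjusted exploratory result at each of two time points.
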